39 institutional resources available. These techniques may vary from conscious sedation to
40 general anesthesia, all of which have been proven to be acceptable methods.

41
42 In this center endometrial ablations are performed as an outpatient procedure
43 under general anesthesia with a variety of induction techniques and intraoperative pain
44 management practices. According to physician preference, patients may receive an

45 additional paracervical injection of local anesthetic before the procedure, immediately
46 after, or not at all. To date, there are no studies evaluating the efficacy of local
47 anesthetic in addition to general anesthesia for patients receiving endometrial ablation
48 to guide physician practice. The purpose of this study is to evaluate the efficacy of local
49 anesthetic, in addition to general anesthesia, in our large, community-based patient
50 population, in meaningfully decreasing postoperative pain.

51
52

53 **Methods:**

54 This study will be a single center prospective single blind randomized controlled
55 trial of premenopausal women undergoing endometrial ablation. This study will take
56 place in the Christiana Hospital outpatient surgical center. Patients will include English
57 speaking premenopausal women aged 30 – 55 scheduled to undergo outpatient
58 endometrial ablation in the surgical center. These patients will be recruited either in
59 physician’s offices, by telephone based on surgical scheduling, or on the day of their
60 procedure. All consents will be signed in person.

61

62 **Study Design:**

63 Frequently, providers will give their patients additional analgesia in the form of a
64 local anesthetic injected as a paracervical block, either before or after the completion of
65 the procedure with the hope of reducing postoperative pain. This practice is not
66 standardized, as its efficacy has never been evaluated in the setting of endometrial
67 ablation under general anesthesia.

68

69 The purpose of this study is to assess the efficacy of this additional local
70 anesthesia upon completion of endometrial ablation under general anesthesia.
71 Patients, once consented, will be randomized in blocks of 6 to either the treatment
72 group or control groups. Those randomized to the treatment group will receive a
73 paracervical injection of 20 mL 0.25% Bupivacaine at the completion of the procedure

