75 equal volume injection of normal saline with the same paracervical technique.
76 Paracervical injection will be standardized to include a total dose of 20 mL divided into
77 four 5 mL injections at the 2, 4, 8, and 10 o’clock positions on the cervix (Howard W.
78 Jones III, 2008). Paracervical block will be given at the completion of the endometrial
79 ablation.

80

81 Only the patients and PACU staff will be blinded to the injected solution. Once
82 general anesthesia has been induced the circulating nurse will open the study patient’s
83 unique randomization sequence and the appropriate study solution will be drawn in the
84 operating room. The endometrial ablation procedure will be performed by the surgeon
85 in accordance with that surgeon’s specific preference for technique and device. Upon
86 completion of the procedure, and before general anesthesia is reversed, the
87 paracervical injection of the patient’s unique study solution will be administered as
88 described above. The operating room team including the surgeon, anesthesiologist, and

[figure not shown]
89 ancillary staff will be aware of the injected solution's contents. The post anesthesia care
90 unit (PACU) staff responsible for assessing immediate and delayed postoperative pain
91 will not be aware of the contents of the injected solution, except when necessary for
92 any unexpected complication, in which case the pharmacist maintaining the
93 randomization coding will break the code for that particular patient. All patients will
94 receive IV Toradol with completion of the procedure and have a standardized rescue
95 analgesia protocol in place in the postoperative care unit setting in accordance with the
96 current practice described above. Per the nursing protocols postoperative pain will be
97 assessed using 10 point Visual Analog Scale (VAS) and if patient's pain is above or equal
98 to a 5, on the 10 point scale, they may receive additional analgesia in the form of
99 intravenous (IV) medication or by mouth tablets (PO). Pain scores, as well as rescue
100 analgesic administered, is routinely recorded by the nursing staff and converted to a
101 patient's electronic health record.

102

103 Due to the infrastructure set up, at CCHS outpatient endometrial ablations are
104 performed under general anesthesia with the patients asleep for the entire procedure.
105 Per the standard surgical center protocol postoperative patients will be assessed

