139 postoperative pain score at 1 hour was 2.85 ± 2.21 . The 40% hypothesized reduction in
140 pain is equivalent to approximately 1 full point on the VAS scale and felt to be a clinically
141 meaningful decrease at the lower end of the VAS scale that could influence policy and
142 practice. The average standard deviation between the mean 1 hour postoperative pain
143 scores between the reviewed charts of the 20 patients receiving a paracervical block
144 and the 20 that do not was 1.78, approximately equal to 75% of the average mean pain
145 scores for the 40 patients who did and did not receive a paracervical block. Using a two
146 tailed test, a Type I error of 5% and statistical power of 80%, and an average standard
147 deviation equal to 75% of the average VAS scores in both groups, the study requires a
148 sample of 36 patients per study group. Assuming a 15% attrition rate this study requires
149 42 patients per study arm (84 total participants). Enrollment in this study will occur for
150 10 months, or until the number of participants needed per study group is met,
151 whichever occurs first. This allows at least 2 months for data analysis and report
152 composition. Enrollment will be monitored by the Principal Investigator ([name])
153 monthly, to gauge when enrollment should stop. To ensure ongoing enrollment of
154 similar numbers of participants in each study group, randomization in blocks of 2 will be
155 used, so that for each 2 patients enrolled, 1 will be assigned to each study group.

156

157 **Secondary outcomes:** The study will also conduct descriptive analyses of the study
158 group differences in postoperative pain scores at 4 and 8 hours following surgery,
159 amount of rescue analgesia required postoperatively, but before discharge, time to
160 discharge, postoperative nausea/vomiting requiring medication, blood loss, and amount
161 of narcotic remaining at postoperative day one.

162

163 **Data Points:**

164 Covariates

165 - age

166 - race/ethnicity

- 167 - Insurance type
- 168 Mediating variables
- 169 - BMI (height/weight)
- 170 - Indication for surgery
- 171 - surgeon (anonymous code)
- 172 - type of ablation
- 173 - cervical dilation
- 174 - type and number of previous surgeries
- 175 - intra-operative complication incidence
- 176 Outcomes
- 177 - 1 hour postop VAS pain score (primary outcome)
- 178 - 4 and 8 hours postop VAS pain score (secondary outcomes)
- 179 - blood loss
- 180 - time to discharge

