- 181 - type and amount of postop opioid given
- 182 -postop anti-emetics given
- 183 - postop complication incidence

184
185

186 **Inclusion criteria:** English speaking premenopausal women, aged 30 – 55, undergoing
187 outpatient endometrial ablation at the CCHS SurgiCenter for menorrhagia, abnormal
188 uterine bleeding, or thickened endometrium.

189

190 **Exclusion criteria:**

- 191 - Known malignancy
- 192 - Weight < 50 Kg
- 193 - Amide allergy
- 194 - History chronic pain
- 195 - Cardiac arrhythmia
- 196 - Dilaudid/codeine allergy
- 197 - History of opioid use
- 198 - Inability to take PO Opioids
- 199 - Uterine anomaly
- 200 - Previous ablation
- 201 - Concomitant laparoscopic surgery
- 202 - Primary language other than English

203

204 **Data analysis:** Continuous variables will be assessed using Student's t-tests and
205 categorical variables will be assessed using the chi-square tests with Fisher's exact
206 significance levels should there be fewer than 5 observations in any cell. Non-
207 parametric tests may be used to compare median values of continuous variables. Linear
208 and logistic regressions will be conducted on continuous and categorical outcomes, to
209 adjust for any unexpected differences in covariates and to describe mediation of effect.
210 All data will be maintained on a CCHS server accessible only to those members of the

211 research team. All information will be coded based on the patients unique study
212 number.

213

214 Works Cited

215 ACOG Committee on Practice Bulletins. (2007, May). *www.acog.org*. Retrieved 09 21,
216 2015, from [http://www.acog.org/Resources-And-Publications/Practice-](http://www.acog.org/Resources-And-Publications/Practice-Bulletins/Committee-on-Practice-Bulletins-Gynecology/Endometrial-Ablation)

217 [Bulletins/Committee-on-Practice-Bulletins-Gynecology/Endometrial-Ablation](http://www.acog.org/Resources-And-Publications/Practice-Bulletins/Committee-on-Practice-Bulletins-Gynecology/Endometrial-Ablation)

218 Anne Lethaby, J. P. (2013). *Endometrial resection and ablation techniques for heavy*
219 *menstrual bleeding* . Retrieved September 2015, from The Cochrane Library:

220 <http://www.thecochranelibrary.com>

221 Cohen, J. (1977). *Statistical power analysis for the behavioral sciences*. New York:

222 Academic press.

224 11). Philadelphia, PA: Wolters Kluwer.

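### The regression is meant to describe mediation through variables that are settled before the injection is given; a lesser gap is that no analysis is named as primary for 1-hour VAS.

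*Combined protocol and SAP*

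**What the plan says.** **Mediation.** Data analysis plans linear and logistic regressions to "adjust for any unexpected differences in covariates and to describe mediation of effect". Data Points separates three covariates (age, race/ethnicity, insurance type) from seven "Mediating variables": BMI, indication for surgery, surgeon, type of ablation, cervical dilation, previous surgeries and intra-operative complications.

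**Timing.** Study Design gives the treatment arm a "paracervical injection of 20 mL 0.25% Bupivacaine at the completion of the procedure" and repeats the timing for the standardised technique: "Paracervical block will be given at the completion of the endometrial" ablation. The allocation is opened earlier. Once "general anesthesia has been induced the circulating nurse will open the study" patient's assignment, and only then does the surgeon carry out the ablation, with technique and device of the surgeon's choosing. The surgeon and anesthesiologist know the solution, and "ancillary staff will be aware of the injected" solution too.

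**Primary outcome.** Data Points marks the 1-hour VAS score as primary. In Data analysis, "Continuous variables will be assessed using" Student's t-tests. Non-parametric tests are optional, with no condition attached, and regression adjusts for covariate differences that are unexpected, a term left undefined. The sample-size text specifies a two-tailed test and does not name which one. No sentence ties one method to the 1-hour score as the deciding analysis.

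**The concern.** A mediator has to be changed by the treatment and then act on the outcome. A characteristic fixed before the injection cannot be changed by it. Regressing pain on arm with and without such a variable, and calling the shift in the arm coefficient mediation, would present something else as a mechanism of the block. For patient characteristics that something is chance imbalance. For type of ablation and cervical dilation it could also be the conduct of an operating team that already knows the arm. That would be a performance bias, and the mediation label would hide it.

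The second concern is freedom of choice. If several results for the 1-hour score are permitted and none is designated, the result reported as the trial's answer could be chosen after the data are seen. The planned 5% error rate would then not be guaranteed.

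**Working it through.** **1. Order of events**

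Study Design gives this sequence: induction, allocation opened, ablation, injection, reversal of anesthesia.

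| Listed mediator | When settled | Can the drug act through it? |
|---|---|---|
| BMI | before surgery | no |
| Indication | before surgery (it is part of eligibility) | no |
| Previous surgeries | before surgery | no |
| Surgeon | before the injection | no |
| Type of ablation | by completion of the ablation | no |
| Cervical dilation | by completion of the ablation | no |
| Intra-operative complications | mostly before the injection; not defined | possible small exception |

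Six of seven therefore fail. The last three rows also concern the procedure, which takes place after the allocation is opened, so knowledge of the arm could influence them.

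**2. The plan's sample size**

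Inputs from Primary Outcome: control mean 2.85, 40% reduction, SD equal to 75% of the average of the two means, two-sided 5%, 80% power.

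- Treated mean 0.60 × 2.85 = 1.71; difference 1.14.
- Average mean (2.85 + 1.71)/2 = 2.28; SD 0.75 × 2.28 = 1.71.
- n per arm = 2 × [1.71 × (1.960 + 0.842)/1.14]² = 35.3, rounded up to 36.

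This reproduces the plan's 36, so the sizing is that of an unadjusted comparison of two means.

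**3. Type I error when one of several results is chosen**

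The documents give no covariate R² and no trigger rule, so both are assumed here: R² of 0, 0.1 or 0.3 from three covariates, and adjustment for any covariate whose arm difference has p < 0.05. Null simulations used 36 per arm and normal scores.

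| Result reported | R² 0 | R² 0.1 | R² 0.3 |
|---|---|---|---|
| Better of t-test and triggered regression | 5.0% | 5.3% | 5.7% |
| Best of those and the rank test | 6.0% | 6.1% | 6.8% |
| Best of those and an always-adjusted regression | 6.8% | 7.5% | 8.6% |

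Any single analysis, including mechanically triggered adjustment, stays between 4.1% and 5.1%. The first two rows come from 8,000 runs (simulation error about 0.25 points) and the third from 20,000 (about 0.2 points). Repeat runs differ by a few tenths of a point. With scores rounded and bounded at 0 to 10, the last row is 6.8%, 7.5% and 8.4%.

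**4. Power with and without three fixed covariates**

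Unadjusted noncentrality is 1.14/(SD × √(2/36)) on 70 df. With three covariates it is divided by √[(1 − R²)(1 + 3/66)], on 67 df. At SD 1.71 the unadjusted value is 2.83, which gives 79.7%.

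| R² (assumed) | 0 | 0.05 | 0.1 | 0.2 | 0.3 |
|---|---|---|---|---|---|
| Adjusted power, SD 1.71 | 77.8% | 79.9% | 82.0% | 86.2% | 90.3% |

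Break-even is at R² of about 0.045. Primary Outcome also reports SDs of 1.78 and 2.21. Unadjusted power is then 76.4% and 57.9%, and three useless covariates lower it to 74.5% and 56.0% by the same formula. The cost is about 2 points at each SD.

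**The case against.** The strongest reply is that a primary analysis can be inferred. The t-test is the stated default for continuous variables, the rank test is only optional, regression has a supplementary purpose, and 36 per arm is what an unadjusted two-mean comparison needs. Adjustment is also not wholly open, because three covariates are listed under that name. This stands. What is missing is a sentence that designates the t-test, a condition for using the rank test, and a definition of an unexpected difference.

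A reader might infer that the plan carries an error rate of up to 8.6%. The documents do not support that. The figure counts an always-adjusted model that Data analysis does not clearly offer, since adjustment there is only for unexpected differences. Even the 6 to 7% requires that the most favourable result be selected.

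A reader might also want a size for the spurious mediation. The plan defines no mediated share, estimand or test, so none can be given. The verb used is only to describe, and the arm comparison of 1-hour VAS is untouched. That limits the consequence but does not make the mediation aim correct, and nothing elsewhere in the document corrects it.

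Finally, it may be tempting to say that regression ought to be the primary analysis. The documents give no evidence that the listed variables predict 1-hour pain, so this is a trade-off for the sponsor.

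**Conclusion.** The mediation aim is wrong as written for six of the seven listed variables. This follows from the order of events in Study Design and needs no numerical assumption. The harm is one of interpretation: imbalance or operating-team behaviour could be reported as a mechanism of the block. The validity of the primary comparison is not affected.

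The unnamed primary analysis is real but smaller. The t-test is the evident default and is valid. Leaving the choice open could raise type I error from 5% to about 6 to 7%, given the assumed R² range, the assumed trigger and selective reporting. It reaches about 8.5% only if an always-adjusted regression is counted as a further option.

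Both points should be corrected before outcome data are seen by arm.

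**What to change.** 1. In Data analysis, delete the mediation purpose for these variables. In Data Points, relabel them as prognostic factors or possible effect modifiers, and label any arm-by-variable interaction exploratory.
2. Do not adjust for type of ablation, cervical dilation or intra-operative complications, which are recorded after the allocation is opened.
3. Name the unadjusted two-sided t-test of 1-hour VAS as the one primary analysis, and make the rank test a sensitivity analysis.
4. Replace imbalance-triggered adjustment with one supportive linear regression of 1-hour VAS on arm and a short covariate set. The set should be recorded before the allocation is opened, fixed in advance and kept whatever the observed balance. The sponsor chooses it, from the three listed covariates or items such as BMI and number of previous surgeries. Categorical items cost one degree of freedom per extra level.
5. The sponsor may make that regression primary if it expects the set to explain more than about 5% of the variance. If it does not, the price with three covariates is about 2 points of power (79.7% to 77.8% at SD 1.71).

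The cost is a few sentences. The variables are already on the data list, and neither the sample size nor the conduct of the trial changes.
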